2.7.2 Adverse events

General common rules for adverse events

All adverse events (AEs) will be coded to a preferred term (PT) and associated primary system organ class (SOC) using the Medical Dictionary for Regulatory Activities (MedDRA) version currently in effect at Sanofi at the time of database lock.

The AEs will be analyzed in the following 3 categories:

- Pre-treatment AEs: AEs that developed, worsened, or became serious during the pre-treatment period
- Treatment-emergent adverse events (TEAEs): AEs that developed, worsened, or became serious during the treatment-emergent period
- Post-treatment AEs: AEs that developed, worsened, or became serious during the post-treatment period

Similarly, the deaths will be analyzed in the pre-treatment, treatment-emergent period and post-treatment periods.

The primary AE analyses will be on TEAEs. Pre-treatment and post-treatment AEs will be described separately.

An AE with incomplete or missing date/time of onset (occurrence, worsening, or becoming serious) will be classified as a TEAE unless there is definitive information to determine it is a pre-treatment or a post-treatment AE.

If the assessment of the relationship to IMP is missing for an AE, this AE will be assumed as related to IMP. Missing severity will be left as missing.

Multiple occurrences of the same event in the same participant will be counted only once in the tables within a treatment phase.

The AE tables will be sorted as indicated in [Table 6](#).

Table 6 - Sorting of AE tables

AE presentation	Sorting rules
SOC and PT	By the internationally agreed SOC order and decreasing frequency of PTs ^a ,

a Sorting will be based on the SAR442970 intervention group

Analysis of all adverse events

The overview of TEAEs with the details below will be generated:

- Any TEAE
- Any treatment-emergent SAE

- Any severe TEAE
- TEAE leading to death
- Any TEAE leading to permanent intervention discontinuation
- Any treatment-emergent AESI
- Any TEAE related to IMP as per the Investigator's judgment

The AE summaries of [Table 7](#) will be generated with number (%) of participants experiencing at least one event and sorted by the internationally agreed SOC order and decreasing frequency of PTs. Sorting will be based on experimental study drug intervention group (see [Table 6](#)).

Table 7 - Analyses of adverse events

Type of AE	MedDRA levels
All TEAE	Primary SOC and PT
TEAE related to IMP as per Investigator's judgement	Primary SOC and PT
TEAE by maximal intensity	Primary SOC and PT
Treatment-emergent SAE	Primary SOC and PT
TEAE leading to permanent intervention discontinuation	Primary SOC and PT
TEAE leading to death ^a	Primary SOC and PT
Pre-treatment AEs	Overview
Post-treatment AEs	Overview

^a Death as an outcome of the AE as reported by the Investigator in the AE page

Analysis of deaths

In addition to the analyses of deaths included in [Table 7](#) the number (%) of participants in the following categories will be provided:

- Deaths during the treatment-emergent period and post-treatment periods
- Deaths in non-exposed participants or randomized but not treated participants

Analysis of adverse events of special interest (AESIs)

Adverse events of special interest (AESIs) will be selected for analyses as indicated in [Table 8](#). Number (%) of participants experiencing at least one event will be provided for each event of interest, by PT if applicable. Tables will be sorted as indicated in [Table 6](#).

Table 8 - Selection of AESIs

AESI	Criteria
Pregnancy	“Pregnancy” or “Partner Pregnancy” ticked on the Pregnancy eCRF page
Symptomatic overdose with IMP	Symptomatic Overdose ticked Yes, with Overdose of Study Treatment ticked Yes on the Overdose eCRF
Significant ALT elevation (ALT>3×ULN)	“ALT increase” and AESI ticked “Yes” on AE eCRF
Any severe or opportunistic viral, bacterial, fungal, or helminthic infection	AESI ticked “Yes” and (CMQsn00235 [Opportunistic infections Narrow] or CMQ10544 [HLGT Helminthic disorders] or CMQ10176 [GLB_INFECTIONS])
Malignancy	AESI ticked “Yes” and CMQsn00090 [Malignancies Narrow]
Systemic or localized allergic reactions that require immediate treatment	AESI ticked “Yes” and CMQsn00214 [Hypersensitivity Narrow]
Reactivation of hepatitis B	AESI ticked “Yes” and CMQ00071 [GLB_HEPATITIS_B]
Demyelinating disorders or progressive multifocal leukoencephalopathy	AESI ticked “Yes” and CMQsn00154 [Demyelination Narrow]
Congestive heart failure	AESI ticked “Yes” and CMQ10064 [Cardiac failure congestive-single PT]
Myocardial infarction	AESI ticked “Yes” and CMQsn00047 [Myocardial infarction Narrow]
Lupus-like reaction or systemic lupus erythematosus	AESI ticked “Yes” and CMQsn00045 [Systemic lupus erythematosus Narrow]

ALT: alanine aminotransferase; ULN: upper limit of normal

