#### **8.4.7 Adverse events of special interest**

An AESI is an AE (serious or nonserious) of scientific and medical concern specific to the Sponsor's product or program, for which ongoing monitoring and immediate notification by the Investigator to the Sponsor is required. Such events may require further investigation in order to characterize and understand them. Adverse events of special interest may be added, modified, or removed during a study by protocol amendment.

- Pregnancy of a female participant entered in a study as well as pregnancy occurring in a female partner of a male participant entered in a study with IMP.
  - Pregnancy occurring in a female participant entered in the clinical trial or in a female partner of a male participant entered in the clinical trial. It will be qualified as an SAE only if it fulfills one of the seriousness criteria (see Appendix 3 [[Section 10.3](#)]).
  - In the event of pregnancy in a female participant, IMP must be discontinued.

- Follow-up of the pregnancy in a female participant or in a female partner of a male participant is mandatory until the outcome has been determined (See [Section 8.4.5](#)).
- Symptomatic overdose (serious or nonserious) with IMP (see definition of an overdose in [Section 6.8](#)).
- Increase in ALT: If increase in ALT  $>3 \times$  ULN, see the “Increase in ALT” flow chart in Appendix 6 ([Section 10.6](#)).
- Other project specific AESI(s)
  - Any severe or opportunistic viral, bacterial, fungal, or helminthic infection whose nature or course may suggest an immunocompromised status and/or any uncommon, unanticipated, or persistent infection (viral, parasitic, bacterial, or fungal; for example, but not limited to tuberculosis, histoplasmosis, listeriosis, coccidioidomycosis, pneumocystis, aspergillosis).
  - Diagnosis of a malignancy during the study.
  - Systemic or localized allergic reactions that require immediate treatment (in the event that a participant has a systemic allergic reaction that requires immediate treatment, blood samples should be withdrawn as soon as feasible [not to interfere with treatment of the reaction] for the analysis of ADA, serum tryptase, C1q, C1 inhibitor, C3 and C4, and repeated at 4 hours and 24 hours).
  - Reactivation of hepatitis B.
  - Demyelinating disorders or progressive multifocal leukoencephalopathy.
  - Congestive heart failure.
  - Myocardial infarction.
  - Lupus-like reaction or systemic lupus erythematosus.

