### **Analysis of all adverse events**

Adverse event incidence table will be provided by treatment group for all types of TEAEs: all TEAEs, all treatment-emergent AESI (defined with a PT or a prespecified grouping), all treatment-emergent SAEs and all TEAEs leading to permanent treatment discontinuation. AEs will be summarized separately for Period A, B, and C.

The AE summaries will be generated with number (%) of participants experiencing at least one event.

Deaths will also be analyzed.

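### In eight of the eleven AESI categories, an event the Investigator ticks as an AESI goes uncounted if its coded term lies outside a named query

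*SAP*

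**What the plan says.** SAP section 2.7.2 makes Table 8 the selection rule: "Adverse events of special interest (AESIs) will be selected for analyses as indicated in" that table. Its eleven rows fall into five groups.

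- **One preferred term (1 row).** Heart failure: the tick and "CMQ10064 [Cardiac failure congestive-single PT".
- **One Narrow search (5 rows).** Malignancy, allergic reactions, demyelination or progressive multifocal leukoencephalopathy (PML), myocardial infarction and lupus, each with the tick. Examples are "AESI ticked “Yes” and CMQsn00047 [Myocardial infarction Narrow" and "AESI ticked “Yes” and CMQsn00154 [Demyelination Narrow".
- **Any of three searches (1 row).** Infection: "AESI ticked “Yes” and (CMQsn00235 [Opportunistic infections Narrow] or CMQ10544 [HLGT Helminthic disorders] or CMQ10176 [GLB_INFECTIONS". Two of the three are not labelled Narrow.
- **One search not labelled Narrow (1 row).** Hepatitis B reactivation, with the tick.
- **No coded query (3 rows).** Pregnancy and symptomatic overdose are taken from boxes on their own eCRF pages. ALT elevation is taken from the AE page entry plus the tick.

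Protocol section 8.4.7 gives the AESI list, including "Congestive heart failure". Protocol section 9.2.6.1 says the analysed AESIs are "defined with a PT or a prespecified grouping" and does not mention a tick. Table 2 of both documents includes AESI incidence in a secondary safety endpoint. The TEAE overview in SAP section 2.7.2 has a line for any treatment-emergent AESI, with no definition of its own.

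**The concern.** Two conditions joined by AND can never count more than either condition alone. An Investigator may judge an event to be an AESI and notify the sponsor at once, as the protocol requires, and the event can still be missing from the AESI table because of how its verbatim term was coded. The plan has no row or rule for that case.

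This runs against the SAP's other adverse event conventions. A missing causality assessment is taken as related, and an unclear onset date is taken as treatment-emergent. There, doubt leads to inclusion. In Table 8, a mismatch between tick and code leads to exclusion.

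At stake is the AESI component of a secondary endpoint. Several of the affected categories (malignancy, demyelinating disease, hepatitis B reactivation, heart failure, lupus-like syndrome) are also listed as potential risks in protocol Table 1. If AESIs are few, one omission could empty a row.

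**Working it through.** The documents give no figure for this point, so there is nothing to reproduce. The check is a row-by-row reading, a comparison of counting rules, and the weight of one participant.

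**Step 1: rows affected.** Rows needing both the tick and a coded query: 5 (Narrow alone) + 1 (single term) + 1 (hepatitis B) + 1 (infection) = 8. Rows with no query: 3. Total 8 + 3 = 11.

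**Step 2: how an event is treated in those eight rows.**

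| Ticked as AESI | Term in query | Table 8 | Protocol 9.2.6.1, read literally | Every ticked AESI counted |
|---|---|---|---|---|
| Yes | Yes | counted | counted | counted |
| Yes | No | not counted | not counted | counted |
| No | Yes | not counted | counted | not counted; listed for review |
| No | No | not counted | not counted | not counted |

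Write T for the ticked events and Q for the query hits. Table 8 counts T∩Q, the literal protocol wording counts Q, and the last column counts T. The shortfall of Table 8 against the Investigators' reports is the number of events in T but not in Q. It is zero or positive, never negative.

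**Step 3: is the tick declared as a change?** SAP section 1 says there are no major changes from the protocol analyses. SAP section 2.10, Table 9, lists one change, to a DLQI endpoint. The tick requirement is not listed.

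**Step 4: the overview line.** It could be programmed from the tick alone (T) or from Table 8 (T∩Q). The sentence that introduces Table 8 points to the second, but the SAP does not say. Under the first reading the overview total could exceed what the category rows support, with no explanation in the outputs.

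**Step 5: where an omitted event still appears.** SAP Table 7 tabulates all TEAEs by system organ class and preferred term, and separately those that are related, serious, fatal or led to discontinuation, as well as TEAEs by maximal intensity. None of these depends on AESI status.

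**Step 6: weight of one participant in Period A.** Planned randomisation is 84 participants at 2:1 (protocol section 4.1).

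- SAR442970: 84 × 2/3 = 56, and 1/56 = 1.8 percentage points.
- Placebo: 84 × 1/3 = 28, and 1/28 = 3.6 percentage points.

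**The case against.** The strongest defence is that the tick does necessary work. Several protocol AESIs are defined clinically: allergic reactions that need immediate treatment, or infections whose course suggests immunocompromise. A coded term cannot express those criteria, and the queries alone would admit events that do not meet them. Immediate Investigator notification is part of the protocol's AESI concept, the queries are prespecified groupings, and the protocol leaves technical detail to the SAP. This stands as an argument for keeping the tick and for not counting unticked query hits automatically. It does not justify discarding an event that was ticked.

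The heart failure row can also be defended. The protocol names congestive heart failure and the chosen term carries that name. Protocol Table 1 names the broader risk of heart failure, but it is not the AESI list. The contents of the queries are not given, so no particular lost event can be shown, for heart failure or for PML under the demyelination search. That also stands. The gap is the lack of any provision for a mismatch.

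Finally, the safety analysis is descriptive, an external IDMC reviews accumulating safety data, and no decision rule depends on this table. That limits the importance of the point but does not remove it.

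A reader might infer that every AESI is subject to a narrow double condition, or that omitted events vanish from the safety endpoint. The documents do not support either. Three rows use no query, the infection and hepatitis B rows are not confined to a Narrow search, and omitted events remain in the general TEAE tables.

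**Conclusion.** The point holds in a limited form. In eight of eleven categories, following Table 8 exactly can leave an Investigator-reported AESI out of the AESI component of a secondary endpoint. Against the ticked events, the error can only be an undercount. The overview line is undefined, and Table 8 and protocol section 9.2.6.1 do not state the same rule.

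The expected number of omissions is unknown, because the documents give neither the query contents nor any tick rates. The only size available is per event: 1.8 percentage points on SAR442970 or 3.6 on placebo for one omitted participant in Period A, assuming 84 participants are randomised 2:1 and all are treated. This should be corrected before the tables are programmed, but no efficacy conclusion or stopping decision turns on it.

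**What to change.** 1. Count every AESI the Investigator ticked. Use the queries only to assign it to a category row.
2. Add a row for ticked AESIs that match no query. This also catches a ticked heart failure event coded to another term, so that query need not be redefined.
3. Define the overview line as any ticked AESI plus the pregnancy and symptomatic overdose events taken from their own eCRF pages.
4. List query hits that were not ticked for medical review, without counting them automatically. The review can be blinded for Period A if done before the Week 16 lock. It cannot be for Period B, which is open-label and for which the study team is unblinded once the Week 16 analysis is run. The SAP already plans blinded medical review of selected medications, so the process exists.
5. Reconcile Table 8 with protocol section 9.2.6.1 and record the difference in SAP Table 9.

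The cost is reprogramming one table and a short review. The downside is that a few more events may be shown.

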2.7.3 Additional safety assessments

2.7.3.1 Laboratory variables, vital signs, and electrocardiograms (ECGs)

The following laboratory variables, vital signs, and electrocardiogram (ECG) variables will be analyzed. They will be converted into standard international units.

- Hematology:
 - Red blood cells and platelets and coagulation: hemoglobin, hematocrit, red blood cell count, platelet count, mean corpuscular volume, mean corpuscular hemoglobin concentration, mean corpuscular hemoglobin and reticulocytes
 - White blood cells: white blood cell count, neutrophils, lymphocytes, monocytes, basophils, eosinophils
- Clinical chemistry:
 - Metabolism: fasting glucose, fasting total cholesterol, fasting triglycerides, fasting high-density lipoprotein, fasting low-density lipoprotein, fasting very low-density lipoprotein, total protein, albumin, creatine phosphokinase
 - Electrolytes: sodium, potassium

- Renal function: creatinine, creatinine clearance, blood urea nitrogen. Creatinine clearance will be derived with the equation of Cockcroft and Gault using weight assessed at the same visit as creatinine.
- Liver function: alanine aminotransferase (ALT)/ Serum glutamic-pyruvic transaminase, aspartate aminotransferase (AST)/ Serum glutamic-oxaloacetic transaminase, alkaline phosphatase, total and direct bilirubin
- Vital signs: heart rate (beats per minute), systolic and diastolic blood pressure (mmHg) in sitting or semi-supine position, weight (kg), respiratory rate, temperature
- ECG variables: heart rate, PR, QRS, QT, and corrected QTcF (according to Fridericia).

Data below the lower limit of quantitation/detection limit (LLOQ) will be replaced by half of the LLOQ, data above the upper limit of quantification will be replaced by ULOQ value.

Quantitative analyses

For laboratory variables, vital signs, and ECG variables above, descriptive statistics for results and changes from baseline will be provided for each analysis window during the on-treatment period. These analyses will be performed using central measurements only (when available) for laboratory variables.

For all parameters, mean changes from baseline with the corresponding standard error will be plotted over time.

Analyses according to PCSA

Potentially clinically significant abnormality (PCSA) analyses will be performed based on the PCSA list currently in effect at Sanofi at the time of the database lock. For parameters for which no PCSA criteria are defined, similar analyses will be done using the normal range, if applicable. For parameters defined as efficacy endpoints, PCSA summaries will not be provided.

Analyses according to PCSA will be performed based on the worst value during the treatment-emergent period, using all measurements (either local or central, either scheduled, nonscheduled or repeated).

For laboratory variables, vital signs, and ECG variables above, the incidence of participants with at least one PCSA during the treatment-emergent period will be summarized regardless of the baseline level and according to the following baseline status categories:

- Normal/missing
- Abnormal according to PCSA criterion or criteria

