| Prior and Concomitant Medications                               | X   | X h, i   | X         | X         | X         | X         | X         | X         | X         | X          | X                | X  | X  | X          | X                | X                | X                |  |   |
| Resume HS Medication if Needed w                     |   |   |           |           |           |           |           |           |           |            |                  |  |  |            |                  | X                |                  |  |   |
| Safety   |   |   |           |           |           |           |           |           |           |            |                  |  |  |            |                  |                  |                  |  |   |
| AE Reporting, Including SAEs                                    | X   | X   | X         | X         | X         | X         | X         | X         | X         | X          | X                | X  | X  | X          | X                | X                | X                |  |   |
| 12-Lead ECG   | X   |   |           |           |           |           |           |           |           |            | X                |  |  |            |                  | X                | X                |  |   |
| Vital Signs x  | X   | X   | X         | X         | X         | X         | X         | X         | X         | X          | X                | X  | X  | X          | X                | X                | X                |  |   |
| Physical Examination (including height and weight) y | X   | X   |           | X         |           | X         |           | X         |           | X          |                  | X  |  | X          |                  | X                | X                |  |   |
| Fasting Lipid Panel z                                | X   | X   |           | X         |           | X         |           |           |           | X          |                  | X  |  |            | X                |                  | X                |  |   |

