| Procedure a                                     | Screening Period (Maximum 4 weeks) b | Treatment Period A: Double-blind Placebo Controlled Study – Primary Efficacy Assessment Window (16 weeks) |           |           |           |           |           |           |           |            |                  | End of Double-blind/ Start of Open Label | Treatment Period B: Open Label Period (12 weeks) |            |                  |                  |                  | End of Open Label/ Start of Safety Follow-Up | Follow-Up Period C: Safety Follow-Up Period (8 weeks after EOT) |
|--|---|---|-----------|-----------|-----------|-----------|-----------|-----------|-----------|------------|------------------|--|--|------------|------------------|------------------|------------------|--|---|
| Visit Number (V) c                              | V1  | V2  | V3        | V4        | V5        | V6        | V7        | V8        | V9        | V10        | V11              | V12                                      | V13  | V14        | V15              |                  |                  |  |   |
| Visit Label  | Screening                                       | Baseline  |           |           |           |           |           |           |           |            |                  |  |  |            |                  | EOT d | EOS d |  |   |
| Visit Weeks e                                   | W-4 to W0                                       | W0  | W2        | W4        | W6        | W8        | W10       | W12       | W14       | W16        | W18 f | W20                                      | W22 f                                 | W24        | W26 f | W28              | W36              |  |   |
| Visit Days   | D-28 to D-1                                     | D1  | D15 (±3d) | D29 (±3d) | D43 (±3d) | D57 (±3d) | D71 (±3d) | D85 (±3d) | D99 (±3d) | D113 (±3d) | D127 (±3d)       | D141 (±3d)                               | D155 (±3d)                                       | D169 (±3d) | D183 (±3d)       | D197 (±3d)       | D253 (±5d)       |  |   |
| Non-fasting Laboratory Testing z                | X   | X   |           | X         |           | X         |           | X         |           | X          |                  | X  |  | X          |                  | X                | X                |  |   |

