- v* All eligible participants will be treated for 28 weeks, receiving a SC administration of IMP or placebo every 2 weeks for the first 14 weeks based on randomization, and then starting at Week 16 (Visit 10) all participants will receive IMP every 2 weeks until the last dose is administered at Week 26 (Visit 15).
- w* Per Investigator discretion, participants may resume treatment for HS as needed (including, but not limited to oral and topical antibiotics, corticosteroids, opioid and non-opioid analgesics, spironolactone, finasteride, or metformin). Participants may also receive unlimited lesion intervention as needed per Investigator discretion.
- x* Vital signs, including body temperature (°C), heart rate (beats per minute), respiratory rate (breaths per minute), and systolic and diastolic blood pressure (mm Hg), will be measured at all visits detailed in the flowchart.
- y* Physical examination will include examination of skin, nasal cavities, eyes, ears, cardiovascular, respiratory, gastrointestinal, neurological, lymphatic, and musculoskeletal systems. A brief symptom-directed physical examination should be performed at other visits if, in the opinion of the Investigator, it is warranted by the participant's AE status or on review of symptoms and will include, at a minimum, assessments of the skin, cardiovascular system, and abdomen (liver and spleen). Height will be measured and recorded at the Screening Visit. Weight will also be measured and recorded at the Screening, Baseline, Week 16, and EOS Visit.
- z* For fasting lipid panel, participant must be fasting for 8 hours prior to laboratory testing (may consume water). If unable to fast, participant may consume a light meal. Labs drawn during non-fasting laboratory testing will include hematology and clinical chemistry only. For laboratory testing please see [Table 12](#).
- aa* Only for WOCBP: serum pregnancy test at Screening (Visit 1) and urine pregnancy tests at every visit from Baseline (Visit 2) to EOS (Visit 17). A negative result must be obtained at Screening (Visit 1) and at Baseline (Visit 2) prior to randomization. In case of positive urine test, the study treatment will be withheld and a serum pregnancy test to confirm the pregnancy should be performed as soon as possible. Pregnancy will lead to definitive treatment discontinuation in all cases.

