#### 8.3.1 Physical examinations

- Physical examination will include examination of skin, nasal cavities, eyes, ears, respiratory, cardiovascular, respiratory, gastrointestinal, neurological, lymphatic, and musculoskeletal systems. Height will be measured and recorded at the Screening Visit. Weight will also be measured and recorded at the screening, Baseline, Week 16, and EOS Visit.
- A brief symptom-directed physical examination should be performed at other visits if, in the opinion of the Investigator, it is warranted by the participant's AE status or on review of symptoms and will include, at a minimum, assessments of the skin, lungs, cardiovascular system, and abdomen (liver and spleen). Investigators should pay special attention to clinical signs related to previous serious illnesses.

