**Table 12 - Protocol-required laboratory tests**

| Laboratory tests         | Parameters  |
|---------------------------------|--|
| Hematology                      | Platelet count
Red blood cell (RBC) count
RBC indices:
Mean corpuscular volume (MCV)
Mean corpuscular hemoglobin (MCH)
%Reticulocytes
White blood cell (WBC) count with differential:
Neutrophils
Lymphocytes
Monocytes
Eosinophils
Basophils
Hemoglobin
Hematocrit   |
| Clinical chemistry a | Blood urea nitrogen (BUN)
Potassium
Creatinine
Fasting glucose
Sodium
Calcium
Aspartate aminotransferase (AST)/ Serum glutamic-oxaloacetic transaminase (SGOT)
Alanine aminotransferase (ALT)/ Serum glutamic-pyruvic transaminase (SGPT)
Alkaline phosphatase b
Total and direct bilirubin
Total protein
Albumin
Creatine phosphokinase  |
| Fasting lipid panel             | Fasting total cholesterol
Fasting triglycerides
Fasting high-density lipoprotein cholesterol
Fasting low-density lipoprotein cholesterol
Fasting very low-density lipoprotein cholesterol  |
| Routine urinalysis              | Specific gravity
pH, glucose, protein, blood, ketones, bilirubin, urobilinogen, nitrite, leukocyte esterase by dipstick   |
| Pregnancy testing               | Microscopic examination (if blood or protein is abnormal)
Serum or highly sensitive urine human chorionic gonadotropin (hCG) pregnancy test (as needed for women of childbearing potential)   |

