2 STATISTICAL ANALYSES

2.1 GENERAL CONSIDERATIONS

In general, continuous data will be summarized using the number of observations available, mean, standard deviation (SD), median, Q1, Q3, minimum, and maximum. Categorical and ordinal data will be summarized using the count and percentage of participants.

The baseline value is defined as the last available value before the first dose of double-blind IMP. For participants randomized but not treated, the baseline value is defined as the last available value before randomization.

Unless otherwise specified, analyses will be performed by intervention group and overall, for baseline and demographics characteristics.

The intervention groups will be presented as follows:

- Period A: SAR442970 150mg q2w and Placebo.
- Period B and Period C: SAR442970 150 mg q2w/SAR442970 150 mg q2w, Placebo/SAR442970 150 mg q2w and overall unless otherwise specified.

Observation period

The observation period will be divided into the following segments:

The pre-treatment period is defined as the period up to first blinded IMP administration.

Period A:

- The **treatment-emergent (TE) period of Period A** is defined as the period from the first blinded IMP administration to the last blinded IMP administration + 75 days or the first open-label IMP administration, whichever occurs earlier. The TE period of Period A includes the following 2 sub-periods:
 - The **on-treatment period of Period A** is defined as the period from the first blinded IMP administration to the last blinded administration of the IMP + 14 days, or the first open-label IMP administration, whichever occurs earlier.
 - The **residual treatment period of Period A** is defined as the period after the end of the on-treatment period of Period A to the end of the TE period of Period A.

Period B:

- The **treatment-emergent (TE) period of Period B** is defined as the period from the first open-label IMP administration to the last open-label IMP administration + 75 days. The TE period of Period B includes the following 2 sub-periods:
 - The **on-treatment period of Period B** is defined as the period from the first open-label IMP administration to the last open-label administration of the IMP + 14 days.

- The **residual treatment period of Period B** is defined as the period after the end of the on-treatment period of Period B to the end of the TE period of Period B.

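### The SAP's same-visit weight rule leaves creatinine clearance derivable, by schedule, at only 2 of 8 post-baseline creatinine visits and at none of the on-treatment Period B visits

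*SAP*

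**What the plan says.** **SAP 2.7.3.1** names creatinine and creatinine clearance as separate renal function variables and gives this rule for the second: "Creatinine clearance will be derived with the equation of Cockcroft and Gault using weight assessed at the same visit as creatinine". The same section plans descriptive statistics and changes from baseline in each on-treatment analysis window. It also plans an analysis of potentially clinically significant abnormalities (PCSA) on the worst treatment-emergent value. Where no PCSA criterion exists, the normal range is used if applicable. SAP Appendix 4 treats a parameter with no measurement in a window as missing for that visit.

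**Protocol, weight.** The footnote to the physical examination row in Section 1.3.1 states: "Weight will also be measured and recorded at the Screening, Baseline, Week 16, and EOS Visit". The US flowchart (Section 1.3.2) carries the same footnote, and Section 8.3.1 repeats it: "Weight will also be measured and recorded at the screening, Baseline, Week 16, and EOS Visit". The row itself, however, is labelled "Physical Examination (including height and weight") and is marked at many more visits.

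**Protocol, creatinine.** Table 12 places creatinine in clinical chemistry. Chemistry is drawn in the row "Non-fasting Laboratory Testing", whose footnote says: "Labs drawn during non-fasting laboratory testing will include hematology and clinical chemistry only".

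**SAP 2.1, Period B.** The on-treatment period "is defined as the period from the first open-label IMP administration to the last open-label administration of the IMP + 14 days". The treatment-emergent period runs to the last open-label dose plus 75 days.

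**The concern.** Cockcroft-Gault needs a weight, and the SAP accepts only one taken at the same visit as the creatinine sample. If weight is scheduled at fewer visits than creatinine, the SAP's own rule turns a measured creatinine into a missing clearance. The incidence of potentially clinically significant laboratory abnormalities is a secondary endpoint, and clearance is one of the listed laboratory variables. A clearance table with no scheduled values for a whole treatment period would not deliver what the SAP promises. A worst-value analysis would draw on far fewer values than the laboratory schedule suggests.

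**Working it through.** The plan gives no figure of its own to reproduce. The check is a cross-match of two schedules, followed by a comparison of study days with the SAP period definitions.

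**1. Cross-match.** The creatinine visits are those marked in the non-fasting laboratory row; the US and non-US flowcharts agree. The weight visits come from the footnotes and Section 8.3.1. Screening and Baseline have both measurements, so they are not affected. The last column shows how old the most recent scheduled weight would be at each visit.

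| Visit | Day | Creatinine | Weight | Same-visit clearance | Age of last scheduled weight |
|---|---|---|---|---|---|
| Week 4 | 29 | yes | no | no | 4 weeks (Baseline) |
| Week 8 | 57 | yes | no | no | 8 weeks (Baseline) |
| Week 12 | 85 | yes | no | no | 12 weeks (Baseline) |
| Week 16 | 113 | yes | yes | yes | 0 |
| Week 20 | 141 | yes | no | no | 4 weeks (Week 16) |
| Week 24 | 169 | yes | no | no | 8 weeks (Week 16) |
| Week 28/EOT | 197 | yes | no | no | 12 weeks (Week 16) |
| Week 36/EOS | 253 | yes | yes | yes | 0 |

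Derivable: 2 of 8. Not derivable: 6 of 8 = 75%.

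**2. Period A.** There are four creatinine visits (Weeks 4, 8, 12, 16). Week 16 belongs to Period A because its safety window closes at the first open-label dose. Derivable: 1 of 4.

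**3. On-treatment Period B.** The last scheduled dose is at Week 26 (Day 183), so the period ends at 183 + 14 = Day 197. Weeks 20, 24 and 28 fall within it (Week 28 on its last nominal day), and none has a scheduled weight. Derivable: 0 of 3.

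**4. Treatment-emergent Period B.** The period ends at 183 + 75 = Day 258. EOS at Day 253 is inside it and is the only visit with a derivable clearance. It falls 253 − 183 = 70 days, or 10 weeks, after the last dose. If the Week 26 dose is missed, the last dose is on Day 169 and the period ends at 169 + 75 = Day 244. EOS on Day 253 then falls outside it, and no scheduled clearance value remains.

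**5. US Week 20 non-responders.** The last dose is on Day 127 and on-treatment ends at 127 + 14 = Day 141. EOS is at about 141 + 56 = Day 197, again 70 days after the last dose. Treatment-emergent ends at 127 + 75 = Day 202. The pattern is the same.

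**6. Could a window supply the weight?** The safety windows in SAP Appendix 4 are separate: Week 12 covers Days 78–91 and Week 16 starts at Day 106. Period B restarts its day count at the first open-label dose. The Week 16 weight therefore serves neither Week 12 nor Week 20.

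**The case against.** **Serum creatinine is still there.** This is the strongest objection, and it stands. Creatinine is its own analysed variable, with by-window summaries, changes from baseline and a worst-value analysis. Within a participant, Cockcroft-Gault clearance moves only with creatinine, weight and age. A reader might infer that a renal signal would go undetected. The documents do not support that: a real fall in clearance would normally appear as a rise in creatinine, which is reported at every laboratory visit.

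**Eligibility and stopping.** A reader might infer that these are compromised. They are not. Exclusion E 28 applies clearance at Screening, where weight is taken, and Section 7.1.1 refers to serum creatinine, which needs no weight.

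**The PCSA consequence is partly unseen.** The sponsor's PCSA list is not in the documents, so whether it has a separate clearance criterion cannot be checked. A reader might also infer that the table would show a falsely low incidence. That depends on a denominator rule the SAP does not state.

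**The row label.** Read literally, it would put weight at every physical examination, and in the non-US flowchart those are the same visits as the laboratory draws. The label cannot be literal, because its own footnote confines height to Screening and weight to four visits, and Section 8.3.1 agrees. SAP 2.7.3.1 also lists weight among vital signs, but the protocol's vital-sign footnote and Section 8.3.2 do not include it. What stands is that a site could follow the label, so the two should be reconciled.

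**Unscheduled weights.** They could fill some gaps, so the counts describe the schedule and not every participant's record.

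**Conclusion.** The point holds for what is scheduled. The SAP states a rule that its own data schedule cannot feed at 6 of 8 post-baseline creatinine visits, and the on-treatment Period B clearance summaries would have no scheduled data at all. Any PCSA or normal-range analysis of clearance in Period B would rest on EOS, about 10 weeks after the last dose.

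This assumes that the weight footnotes and Section 8.3.1 govern over the row label, that visits occur on their nominal days, and that no unscheduled weights are taken.

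The consequence is limited. It is a gap in one derived, descriptive safety variable, and the safety analyses involve no statistical testing. It is worth correcting before programming because the rule discards information the trial already collects.

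**What to change.** Change the sentence in SAP 2.7.3.1 so that clearance uses the last weight recorded on or before the creatinine sample date. This makes clearance derivable at 8 of 8 post-baseline creatinine visits, and at 3 of 3 on-treatment Period B visits, with no new data collection.

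Separately, reconcile the Schedule of Activities row label on height and weight with its footnote in both flowcharts, so that sites and programmers read the same weight schedule.

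Cost: one SAP sentence and a small programming change, plus an editorial correction to the protocol. The downside is that the carried weight can be up to 12 weeks old by schedule. Clearance is proportional to weight in Cockcroft-Gault, so a 3% weight change that is not captured shifts the derived clearance by 3%. A footnote to the clearance tables saying which weight was used would make this visible.
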